IP more rapidly in the first month of life compared with cow milk-based formula in term (35) and in preterm neonates (36).

[figure not shown]
***NEC and its pathogenesis:*** NEC, a life-threatening, GI emergency characterized by increased IP, affects approximately 7 to 10% of preterm neonates, and typically occurs within 7 to 14 days of birth (37, 38) with mortality as high as 30-50% (39). NEC symptoms mainly involve GI dysfunction, such as abdominal distension and feeding intolerance, but the presentation can be non-specific with few warning signs. Current therapies may be invasive, including surgical interventions that are often ineffective due to the rapid progression of the disease. Prematurity is the greatest risk factor for development of NEC (40, 41), due to physiological immaturity of the GI tract and altered levels of the normal GI microbiota. Several studies suggest that the initiation of an intense systemic and local inflammatory cascade leads to intestinal necrosis (42-47). Antenatal exposure to infection/inflammation may predispose the developing intestinal mucosa to subsequent injury or dysregulated inflammatory responses. Previous studies have linked presence of amniotic fluid infection/elevated cytokines, (48) cord blood cytokines, (49, 50) and umbilical cord inflammation (51) with risk for NEC in preterm neonates. In a rat model of NEC, maternal prenatal exposure to microbial LPS led to increased frequency and severity of intestinal injury (52). Taken together, these observations suggest that intestinal injury may be initiated *in utero* and contributes to increased IP at birth in the preterm neonate. Many of the defense mechanisms present in the mature intestine, such as peristalsis and tight junctions between intestinal epithelial cells (37) are decreased in an immature intestine, and thus bacteria normally confined to the intestinal lumen are able to reach systemic organs and tissues. Bacterial translocation triggers the activation of an exaggerated inflammatory response, which leads to further epithelial damage.

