### 2.3 Preliminary Data

[figure not shown]

**Figure 1.** Microbial community diversity and intestinal permeability at study time points day 1, 8, and 15 for a cohort of 43 preterm infants (<33 weeks gestational age). Microbial community diversity is calculated as OTU richness based on 16S rRNA gene amplicon high-throughput sequencing. Intestinal permeability was calculated as the ratio of non-metabolized sugar probes

gestational age (<31.7wk) were identified to be the most discriminatory features for elevated IP by supervised learning scheme, reaching an accuracy of 86.1%. (5) *Clostridiales* and *Bifidobacteriales* are the most abundant bacteria groups in later stages (phase II/III at 6-18

Our analysis of the initial cohort of 43 preterm infants recruited for the IND protocol, and others' previous studies have shown that IP is high at birth in preterms (<33wk gestation) with a rapid maturation of the intestinal barrier over the first 2 weeks. However, in some infants, high IP persisted and/or recurred in association with altered levels of the normal microbiota (bacteria community composition). Specifically, we observed that (1) rapid maturation of intestinal barrier function, characterized by decreased IP, correlates with increased microbial community diversity (Figure 1), and most outstandingly, the increased abundance of beneficial bacteria *Clostridiales* (Figure 2); (2) *Clostridiales* is highly transcriptionally active and co-active with the probiotic bacterium *Bifidobacterium*; (3) neonatal factors, including early introduction of breast milk, shorter period of antibiotic exposure, and later gestational age, favor the early colonization of the gut microbiota by members of *Clostridiales* and *Bifidobacterium*, which altogether are associated with improved intestinal barrier in preterm infants; (4) low *Clostridiales* spp. abundance (<5%) and early

months of age) as shown in Figure 2, suggesting a process of gaining prosperity of these two bacterial groups during intestine development after birth. Altogether our preliminary results suggest the early colonization of the natural occurring probiotics strains *Clostridiales* and *Bifidobacterium* strongly associate with rapid maturation of intestinal barrier function, and their measurement are highly promising for early detection and as potential nutritional supplement to prevent NEC in the high-risk preterm population.

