#### **6.5 Follow-up Visit(s) (include allowable time window)**

*Not applicable.*

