#### **6.8 Final Study Visit (include allowable time window)**

##### **PND21 (± 2d) or discharge/transfer whichever comes first**

- ∞ *Final collection of stool samples for analysis*
- ∞ Medication history including the number of packed red blood cell transfusions and total volume received will be collected from the chart
- ∞ *Record daily weight, and weekly height, and head circumference.*
- ∞ Collection of adverse events from medical chart.

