## **7.3 Safety Reporting Requirements**

### **7.3.1 Reporting Interval**

Document all adverse events (AEs) and SAEs from enrollment through PND21.

All SAEs will be followed until resolution even if this extends beyond the study-reporting period. Resolution of an adverse event is defined as the return to pre-treatment status or stabilization of the condition with the expectation that it will remain chronic.

The investigator will follow all SAEs until resolution (return to pretreatment status or stabilization of the condition with the expectation that it will remain chronic) even if this extends beyond the study-reporting period.

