### **7.6 Halting Criteria/Rules**

#### **7.6.1 Stopping Rules for Individual Subjects**

A pre-dose checklist for evidence of feeding intolerance will be completed prior to La/Rh administration. The Lactulose/Rhamnose administration will be re-scheduled within the study window if the clinically indicated gastric residual is obtained and measures >50% of the previous nutritive feeding volume, and/or contains bile or gross blood, or is hemoccult-positive. If these GI signs are present throughout the study window, the La/Rh test will not be administered. Other conditions that would result in delay or discontinuation of the La/Rh test include hypotension requiring pharmacologic support, clinical or radiographic signs of intestinal ileus or NEC. The subject will continued to be followed until postnatal day 21±2 d or discharge/transfer which ever occurs first.

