**Plans for Study Interruption Based on Safety Monitoring:**

Since the expected in-hospital mortality rate for infants 24-32 weeks gestation is 10-15% at the UMMC NICU, 5-8 deaths may occur in our study population per year. If more than 10 deaths or 7 confirmed cases of NEC >Stage 2 occur within one year or more than 4 deaths or 3 confirmed NEC cases >Stage 2 in consecutively recruited subjects occur within 30 d of enrollment, the study will be interrupted until reviewed by the safety monitor. The study may also be halted if the number of SAEs overall, the number of occurrences of a particular type of SAE, severe AEs/reactions, or increased frequency of events warrant further investigation. The safety review may require temporary suspension of enrollment or all study interventions. The safety review may determine whether the study should continue per protocol, proceed with caution, be further investigated, be discontinued, or be modified and then proceed. Subsequent review of serious, unexpected, and related AEs by the medical monitor, IRB, the sponsor(s), or relevant local regulatory authorities may also result in suspension of further trial interventions at a site. The study sponsor(s) retain the authority to suspend additional enrollment and study interventions for the entire study, as applicable.

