## 8 CLINICAL MANAGEMENT OF EVENTS

### 8.1 Adverse Event Management

Study interventions will not influence medical care. Morbidities associated with prematurity are protocol-specified potential serious adverse events. These are events that are anticipated to occur in the preterm population even in the absence of study intervention. Morbidities of prematurity will be recorded on CRFs on study day 21 or discharge/transfer whichever comes first.

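### The 30-day interruption trigger in section 7.6 runs past PND21, where required capture of new events ends, so it can undercount

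*Combined protocol and SAP*

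**What the plan says.** The study-level rule in section 7.6 (Plans for Study Interruption Based on Safety Monitoring) has an annual trigger and a second one, which applies if "more than 4 deaths or 3 confirmed NEC cases >Stage 2 in consecutively recruited subjects occur within 30 d of enrollment". Section 4.1 admits infants at less than 5 days of age.

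The provisions on capture and follow-up use other end points:

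- Section 7.3.1, which sets the reporting interval: "Document all adverse events (AEs) and SAEs from enrollment through PND21". It adds that serious events are followed until they resolve, even past that interval.
- Section 6.8, the final visit and the last collection of adverse events from the chart: "PND21 (± 2d) or discharge/transfer whichever comes first".
- Section 7.6.1, on stopping for individual infants, says the subject is "followed until postnatal day 21±2 d or discharge/transfer which ever occurs first".
- Appendix A: the last column of the schedule is day of life 21.
- Protocol Summary: subject participation is 28 days.

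**The concern.** A numerical trigger can work as written only if the study must collect the events it counts. Here the counting period is tied to enrolment and lasts 30 days, while the duty to record new events is tied to birth and stops at PND21. No section asks anyone to look for a new death or a new NEC case between those two points.

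The error can go one way only. An unrecorded event can keep the trigger from firing, but cannot make it fire falsely. This matters because section 7.6 holds the only numerical study-level triggers. Section 7.5.1, on interruption for all subjects, is marked not applicable, no interim analysis is planned, and section 7.5 makes the sponsor-investigator the data safety monitor. A preset rule in that setting should be answerable from required data.

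**Working it through.** The plan gives no figure of its own to reproduce; the check is a comparison of dates.

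**Inputs.** Age at enrolment: under 5 days, taken as PND0 to PND4 (section 4.1). Trigger window: 30 days from enrolment (section 7.6). End of required capture: PND21 (section 7.3.1), or PND19 to PND23 if the visit tolerance in section 6.8 governs. Participation: 28 days (Protocol Summary).

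**End of the trigger window** = age at enrolment + 30.
- Enrolled at PND0: 0 + 30 = PND30.
- Enrolled at PND4: 4 + 30 = PND34.

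**Uncaptured days** = end of window − end of capture, for an infant still in the unit.

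| Capture ends | Enrolled PND0 | Enrolled PND4 |
|---|---|---|
| PND21 (7.3.1) | 30 − 21 = 9 | 34 − 21 = 13 |
| PND23 (6.8, late) | 30 − 23 = 7 | 34 − 23 = 11 |
| PND19 (6.8, early) | 30 − 19 = 11 | 34 − 19 = 15 |

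On the section 7.3.1 end point the gap is 9/30 = 30% to 13/30 = 43% of the window in calendar time. If the day of birth is numbered PND1, the window ends at PND31 to PND35 and the gap is 10 to 14 days.

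**Does the 28-day participation close the gap?** Counted from enrolment it stops 30 − 28 = 2 days short. Counted from birth it stops 30 − 28 = 2 to 34 − 28 = 6 days short. It also runs past PND21, so it agrees with neither limit.

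**Do the capture provisions agree with each other?** Section 7.3.1 has no tolerance and no exception for infants who leave. Sections 6.8 and 7.6.1 have both. An infant discharged before PND21 is therefore inside the reporting interval of section 7.3.1 but past the final visit of section 6.8.

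**What lies inside capture.** Section 2.1 says NEC "typically occurs within 7 to 14 days of birth", which is before PND21. The sugar dose is given at 7 to 10 days (section 6.9), so 21 − 10 = 11 to 21 − 7 = 14 days of capture follow it if the infant stays in the unit.

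**The case against.** The strongest reply is that little is lost in practice. A death after PND21 from a serious event documented by PND21 should be known, because section 7.3.1 follows such events to resolution. Typical NEC onset is inside capture. The infants are inpatients at one site and adverse events are read from the chart, so the absence of follow-up visits does not by itself prevent a later look. Section 7.6 also lets the study be halted on judgement if events become more frequent. All of this stands, and it limits the effect. It does not remove the mismatch: an infant with no serious event by PND21 can die or develop NEC within 30 days of enrolment without any duty to record it, and the discretionary clause adds no capture.

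It is also fair to say that the discharge or transfer limit is not in section 7.3.1, and that the follow-up sentence in section 7.6.1 comes directly after text on infants whose sugar test is delayed or not given, so it may apply only to them. The end of capture is therefore itself unsettled, and the PND19 and early-discharge cases depend on section 6.8 governing.

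Three stronger readings are not supported:

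- A reader might take 30% to 43% as the share of events missed. These are calendar days. The documents give no rate of deaths or NEC between PND21 and PND34.
- A reader might see a third clock in section 8.1: "Morbidities of prematurity will be recorded on CRFs on study day 21 or discharge/transfer whichever comes first". The protocol does not define that study day for the current schedule, and it may be loose wording for PND21.
- A reader might conclude that the 5 to 8 deaths a year expected in section 7.6 is wrong for the enlarged cohort. At 10% to 15% mortality it corresponds to 5/0.10 = 50 to 8/0.15 = 53 infants a year, but no annual accrual is stated for that cohort, so no error can be shown.

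**Conclusion.** The inconsistency is real. Followed exactly as written, the protocol does not require new deaths and NEC cases to be captured over the last 9 to 13 days of the trigger window (7 to 15 days across the visit tolerance in section 6.8, and longer after early discharge or transfer if that limit applies). The trigger cannot be fully evaluated and can undercount.

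The result assumes enrolment at PND0 to PND4 and that no requirement outside this document extends capture. It concerns new events only. The practical effect is probably small for NEC and is unknown for deaths; the number of missed events cannot be estimated. No endpoint or analysis is affected. It should still be corrected, because it weakens a preset safety rule and is cheap to put right.

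**What to change.** Reconcile the participation period in the Protocol Summary, sections 6.8, 7.3.1, 7.6.1 and 7.6, and Appendix A, so that the period over which the trigger counts deaths and NEC is the period over which the study must capture them. In the same edit, state one end point for capture, including whether the visit tolerance applies, and say how infants discharged or transferred earlier are counted. Which period to use is for the clinical team; no window or threshold is proposed here.

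The cost is protocol wording. If the 30-day window is kept, it adds one later chart check per infant. For infants who have left the unit the site chart may not be enough, and outside records may be needed.

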## 8 CLINICAL MANAGEMENT OF EVENTS

### 8.1 Adverse Event Management

Study interventions will not influence medical care. Morbidities associated with prematurity are protocol-specified potential serious adverse events. These are events that are anticipated to occur in the preterm population even in the absence of study intervention. Morbidities of prematurity will be recorded on CRFs on study day 21 or discharge/transfer whichever comes first.

#### 8.1.1 Temporary Interruption of Study Product in an Individual Subject

*Not applicable.*

#### 8.2 Pregnancy (*if applicable*)

*Not applicable.*

## **9 CLINICAL MONITORING/SITE MONITORING PLAN**

In general, site monitoring is conducted to ensure that:

- ∞ human subjects' rights and well-being are protected;
- ∞ data are accurate, complete, and verifiable from source documents;
- ∞ the study complies with the protocol/amendment(s), ICH Good Clinical Practice (GCP) guidelines, and applicable regulatory requirements.

The internal monitoring plan will be conducted according to the Quality Management plan in Appendix C.

## 10 STATISTICAL CONSIDERATIONS

### 10.5 Sample Size Considerations

Sample size for primary objective: The sample size for the first aim (50 subjects) will provide good precision in the estimate of the distribution of levels of intestinal permeability at each time point. The quantiles will be accurate +/- 10 percentage points (based on a 95% confidence interval). Based on the sites' combined annual admission numbers and survival rates, we expect 120 infants to be eligible in the 6 month planned enrollment period in the first year. The combined NICU population is approximately 59% male with an ethnic distribution of 65% African-American, 33% Caucasian and 2% other.

Sample size for microbiome analysis: The sample size of 200 was calculated to obtain high precision in correlations between features of the stool microbiota and intestinal permeability (IP). Since 83% subjects in the first cohort had high IP ( $La/Rh \geq 0.05$ ) at study day 8, a sample size of 166-236 provides marginal error of 0.05 (maximum sampling error of 5%) and alpha of 0.05 (95% confidence level) to detect correlations between features of the microbiota and changes in IP and to achieve an expected sensitivity of 0.8-0.9 and expected specificity at 0.9-0.95.

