We propose in this study to recruit additional 157 preterm subjects and to combine with our existing 43 preterm subjects to form a statistically powered cohort at 200 (justified in study size analysis in research design), to address our hypothesis that the two naturally occurring beneficial bacteria *Clostridiales* and *Bifidobacterium* are rapidly gaining prosperity during normal intestine development in association with improved barrier function measured by La/Rh ratio. Overall, this continuation of the initial study builds on the previous findings that identified commensal bacteria *Clostridiales* and *Bifidobacterium* species as a strong indicator to the lowered IP and rapid maturation of intestinal barrier, to substantiate measurement of these probiotic strains combined with associated neonatal factors to form an accurate, rapid detection of intestinal permeability abnormality.

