### **2.5 Study Objectives**

The proposed study will evaluate the intestinal permeability measured by the urinary La/Rh ratio at one timepoint between d7-10 of life in 200 preterm infants 24-32 weeks gestation in preparation for a future study of probiotics to improve intestinal permeability in this population.

**Primary Objective:** To estimate mean, variance, and quantiles in IP measured by urinary Lactulose/Rhamnose ratio at 7-10d of life in neonates born between 24 and 32 weeks of gestational age.

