#### **6.9 Product Administration (include allowable time windows)**

Each enrolled preterm neonates will be administered a 1 mL/kg La/Rh solution (8.6 g of lactulose + 140 mg of rhamnose/100 mL) via a clinically indicated OG or NG tube once between 7-10 d of age. The La/Rh solution will be administered by gavage with an enteral feed. Total volume of La/Rh ingested will be recorded. Urine will be collected for a 4-hour period *with cotton balls*. Total volume of urine during the 4 hour collection will be recorded. The urine will be aliquoted and 4 ml of urine saved for analysis. Nursing staff in the NICU will be trained in the procedures prior to study initiation. Only trained NICU staff will be allowed to be responsible for administering the La/Rh solution and collecting the urine. A minimum of 2 ml of urine will be collected. If urine leaks around the cotton balls, then the diaper will be weighed and the diaper weight will be used to estimate the urine volume for the 4 hour collection period. If less than 2 ml urine is collected, then the test will be repeated on another day within the 7-10d window by

administering 1 ml/kg La/Rh solution (8.6g of lactulose + 140 mg of rhamnose/100mL) via an OG/NG tube followed by a 4 hour urine collection. The urine will be stored at -80°C until processed. The sugars will then be measured in urine by HPLC.

Urine La and Rh will be measured in the lab of our collaborator [name] from the University of Calgary, Canada.

*Stool calprotectin, sIgA, and lactoferrin will be measured by commercial ELISA kits.*

Rescue Therapy- NA

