### 10.5 Safety Review *(if applicable)*

## 10.6 Final Analysis Plan

**Primary Objective:** To estimate mean, variance, and quantiles in IP measured by urinary Lacutlose/Rhamnose ratio in in neonates born between 24 and 32 weeks of gestational age.

Sample quantiles of the distribution of IP (as measured by urine LA/Rh ratio) will be calculated at each time point. In addition, we will use mixed effects models to estimate the mean and variance of urine La/Rh. By including other terms in the model we will be able to assess whether high IP (La/Rh ratio  $>0.05$ ) is affected by gestational age, birthweight, sex or *feeding type (mother's own breast milk only, donor breastmilk, preterm formula only, or both breast milk and preterm formula).*

**Secondary Objective:** To evaluate the performance of stool calprotectin, sIgA, and lactoferrin as markers for intestinal permeability *in vivo* as established by the gold standard urine La/Rh in preterm neonates.

**Assessing the relationships between stool markers and urine La/Rh ratio:** To quantify the association between stool calprotectin, sIgA, and lactoferrin, and urine La/Rh ratio, we will calculate Pearson Correlation Coefficients. If the distribution of either variable exhibits substantial skewness we will substitute Spearman Correlation Coefficients. In addition, we will perform sub-group analyses by gestational age or birthweight.

**Assessing the sensitivity and specificity of calprotectin, sIgA, and lactoferrin for identifying children with leaky gut syndrome using an ROC analysis.** Leaky gut syndrome will be defined as having a urinary La/Rh ratio of greater than 0.05 at 7-10 d (12). Using this definition, we will assess the sensitivity, specificity, and predictive value of calprotectin, sIgA, and lactoferrin on each day for identifying those with leaky gut syndrome. An analogous calculation will be made to estimate specificity. We will perform these calculations for a large range of cut-offs for the stool markers, and summarize the findings using an ROC curve. The area under the ROC curve (AUC) will be calculated using an empirical approach to provide an overall summary measure of the performance of **calprotectin, sIgA, and lactoferrin** as measures for leaky gut syndrome.

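### The precision stated for the primary objective (±10 points, 50 subjects, each time point) is too optimistic for central quantiles at n = 50 and was not restated for 200 infants measured once

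*Combined protocol and SAP*

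**What the plan says.** Section 2.5 sets the primary objective: the mean, the variance and the quantiles of the La/Rh ratio at 7–10 days of life. It places the measurement "at one timepoint between d7-10 of life in 200 preterm infants 24-32 weeks gestation". The protocol summary and Section 4 also give 200 infants. Section 2.3 explains how that total is reached: 157 new infants are recruited to "combine with our existing 43 preterm subjects to form a statistically powered cohort at 200".

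Section 10.5 Sample Size Considerations has two paragraphs. The one for the primary objective states: "The sample size for the first aim (50 subjects) will provide good precision in the estimate of the distribution". It refers this to each time point and continues: "The quantiles will be accurate +/- 10 percentage points (based on a 95% confidence interval". It does not limit the claim to particular quantiles. The second paragraph justifies 200 for the microbiome analysis, with a margin of 0.05 for n = 166–236 and expected sensitivity and specificity. It gives no precision for the La/Rh distribution itself.

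Section 10.6 Final Analysis Plan plans the same quantiles: "Sample quantiles of the distribution of IP (as measured by urine LA/Rh ratio) will be calculated at each time point".

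**The concern.** For an objective that is pure estimation, the precision statement is the sample-size justification. Here it has two faults.

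- **The figure.** ±10 points at 95% confidence looks too small for 50 subjects, except in the tails.
- **The design it describes.** Neither the 50 subjects nor the several time points belong to the current study, which has 200 infants and one La/Rh test.

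Section 2.5 says the study prepares for a future probiotic study. A reader planning that study from Section 10.5 would take away the wrong precision, the wrong n and the wrong measurement schedule.

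**Working it through.** **Inputs.** n = 50, ±10 points and 95% confidence come from Section 10.5. N = 200 and one time point come from Section 2.5. The split into 157 new and 43 existing infants comes from Section 2.3.

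**Formula.** The precision of a sample quantile in percentage points is the binomial half-width on the percentile scale, with q the quantile:

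half-width = 1.96 × √(q(1 − q)/n)

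**The plan's own figure, n = 50.**

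- Median: 1.96 × √(0.25/50) = 0.139
- Quartiles: 1.96 × √(0.1875/50) = 0.120
- 15th/85th percentiles: 1.96 × √(0.1275/50) = 0.099
- 10th/90th percentiles: 1.96 × √(0.09/50) = 0.083

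The half-width equals 0.10 at q = 0.154 and q = 0.846. The stated ±10 is therefore met in the outer parts of the distribution and missed across roughly the central 70%, which includes the median and quartiles.

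**Sample size that ±10 would need.** n = 1.96² × q(1 − q)/0.10². At the median this is 96.04, rounded up to 97. At the quartiles it is 72.03, rounded up to 73.

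**Does another method rescue ±10 at the median with n = 50?** No.

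- Wilson gives 13.4, Clopper-Pearson 14.5 and the continuity-corrected interval 14.9.
- The exact order-statistic interval runs from rank 18 to rank 33 (36th to 66th percentile, coverage 0.967). Narrowing it by one rank at each end drops coverage to 0.935.
- A 90% interval, or a one-sided 95% bound, still gives 11.6.
- A simultaneous (DKW) band gives 19.2.

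**Current design.** Half-widths in percentage points:

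| Evaluable infants | Median | Quartiles | 10th/90th |
|---|---|---|---|
| 200 | 6.9 | 6.0 | 4.2 |
| 180 (assumed) | 7.3 | 6.3 | 4.4 |
| 157 (new infants only) | 7.8 | 6.8 | 4.7 |
| 150 (assumed) | 8.0 | 6.9 | 4.8 |

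At N = 200 the exact interval for the median is rank 86 to rank 115 (coverage 0.960), that is, the 43rd to 57.5th percentile.

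**Missing tests.** The rows for 180 and 150 allow for results that never arrive. Section 7.6.1 says "If these GI signs are present throughout the study window, the La/Rh test will not be administered". Section 6.9 says "If less than 2 ml urine is collected, then the test will be repeated on another day", but a repeat within the window may also fail. Section 4.5.2 replaces only withdrawals and deaths. The documents give no expected rate, so both counts are assumptions.

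**Twins.** Section 4.2 excludes only triplets and higher-order multiples, so twin pairs can enrol. The design effect is 1 + pρ, with p the share of infants in enrolled pairs and ρ the within-pair correlation. The documents give neither. Assuming p = 0.1–0.3 and ρ = 0.3–0.5, it runs from 1.03 to 1.15. The median half-width becomes 7.0–7.4 with 200 evaluable infants and 8.1–8.6 with 150.

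Every scenario for the current design stays within ±10.

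**The case against.** The strongest reply is that this is harmless leftover text. The 50-subject sentence belongs to a first stage that has already produced its 43 infants. At 200 infants ±10 is a conservative bound at every quantile, and no decision depends on it. It is also not wrong everywhere at n = 50: the first cohort had 83% with high permeability, which puts the 0.05 cut-off near the 17th percentile, where the half-width at n = 50 is 10.4. The phrase about each time point could refer to the first cohort, which was measured at "study time points day 1, 8, and 15 for a cohort of 43 preterm infants".

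Much of this stands as a limit on the consequence. The primary objective is adequately sized, and the error at n = 50 concerns central quantiles only. It does not remove the point. The sentence is current text, it carries no restriction to outer quantiles, and it is the only precision given for the primary objective. The 0.05 margin in the next paragraph does not fill the gap: it is labelled for the microbiome analysis and would not hold at the median with 200 infants (6.9). Nor does the first-cohort schedule explain Section 10.6, because Section 2.5 ties the primary objective to one measurement at days 7–10.

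Two further remarks are fair. First, study day 8 in the first cohort is only approximately postnatal days 7–10, and this is why figures for 157 infants are given beside those for 200. Second, the objective also covers the mean and variance, for which the plan gives no precision. The documents give no standard deviation of La/Rh from which to derive one.

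**Conclusion.** The precision statement is wrong as written. For the n it names, ±10 points fails at the median (±13.9) and quartiles (±12.0) and holds only outside about the 15th to 85th percentiles. For the current design it is not the actual precision, which is at most about ±6.9 with 200 evaluable infants and ±7.8 with 157. These figures treat infants as independent and refer to the percentile scale, not to La/Rh units. The allowances for missing tests and twin pairs rest on assumed inputs and reach ±8.6 at most. The consequence is modest: no change of sample size or conduct is needed, but the sample-size section and the analysis plan should describe the measurement that the study actually makes.

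**What to change.** In Section 10.5, replace the first two sentences of the primary-objective paragraph with:

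> With 200 infants with an evaluable La/Rh ratio at the day 7–10 measurement (study day 8 for the 43 infants of the first cohort), sample quantiles are accurate to about ±7 percentage points at the median, ±6 at the quartiles and ±4 at the 10th/90th percentiles (95% CI, treating infants as independent). With 157 evaluable infants the figures are about ±8, ±7 and ±5. Missing tests and twin pairs would widen these somewhat.

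In Section 10.6, refer the sample quantiles to the day 7–10 measurement instead of each time point. If the first cohort's days 1 and 15 are also to be summarised, say so separately as a description of those 43 infants, where the half-width at the median is ±14.9.

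The cost is two sentences and one phrase, with no design change. The rest of the same paragraph (120 eligible infants, a six-month enrolment period, combined sites) also predates the single-site study and can be checked in the same edit.
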